14.1.4 Laboratory Test Abnormalities

For laboratory test abnormalities that meet the definition of an SAE, that required the participant to have the investigational product discontinued or interrupted or required the participant to receive specific corrective therapy, the clinical diagnosis rather than the laboratory term will be used by the reporting investigator (e.g., anemia versus low hemoglobin value).

14.1.5 Assessment of Causal Relationship

A medically qualified investigator must assess the relationship of any AE to the use of study drug, based on available information, using the following guidelines:

- **Not related:** There is not a reasonable causal relationship to the investigational product and the adverse event.
- **Unlikely related:** No temporal association or the cause of the event has been identified, or the drug or biologic cannot be implicated.
- **Possibly related:** There is reasonable evidence to suggest a causal relationship between the drug and adverse event.
- Related: There is evidence to suggest a causal relationship, and the influence of other factors is unlikely.

14.1.6 Assessment of Adverse Event Severity

The determination of adverse event severity rests on medical judgment of a medically qualified Investigator. The severity of AEs will be graded using the following definitions:

- **Mild:** Awareness of sign, symptom, or event, but easily tolerated.
- **Moderate:** Discomfort enough to cause interference with usual activity and may warrant intervention.
- **Severe:** Incapacitating with inability to do usual activities or significantly affects clinical status, and warrants intervention.

Anticipated Disease Related Events and Events of Interest

The following are anticipated, disease-related events in patients with LVAD or anticipated events of interest in patients with apixaban or warfarin:

- Arrhythmias
- Cardiac Transplantation
- Device Explant
- Infection
- Transient Ischemic Attack
- Unplanned hospitalization, ER visit or clinic visit

Anticipated events will not be captured as AEs/SAEs during the study but will be entered on the appropriate electronic case report form (eCRF) module ("Anticipated Disease Related Events" page).

14.1.7 Recording and Reporting of Adverse Events

The site Investigator is responsible for monitoring the safety of participants enrolled into the study at the study sites. For this study, non-serious AEs will not be collected on the safety reporting page of the eCRF but should be documented in the source documents and followed according to local standard of care. Events significant enough to necessitate modification of antithrombotic therapy dosing will be captured on the appropriate eCRF module ("Adverse Events" page).

14.1.8 Subject Stopping Criteria and Drug Modification

For patients in the apixaban arm with a thromboembolic event (stroke, device thrombosis or arterial non-CNS thromboembolism), will be considered a study drug failure and converted to warfarin (withdrawn from active treatment). For patients experiencing a bleeding event, the aspirin will be discontinued. Only in patients with recurrent bleeding will the apixaban be discontinued (withdrawn from active treatment) and warfarin initiated at an INR goal of 1.5 to 2.0. Patients will continue to be followed per the study schedule through study completion.

For apixaban patients listed for transplant, who are upgraded to a status 1-3, the apixaban will be discontinued and the patient converted to warfarin. These patients will be followed until transplant or study completion. Each apixaban patient who does not complete the 6-month study duration will be replaced to ensure 20 patients are in the apixaban arm with complete follow-up.

For patients in the warfarin arm with a thromboembolic event, will be managed with a higher INR goal of 2.5 to 3.0. For patients experiencing a bleeding event, the aspirin will be discontinued. Only in patients with recurrent bleeding will the INR goal range be reduced to 1.5 to 2.0. For patients with a 3rd bleeding event, warfarin will be stopped, and the patient will be withdrawn from treatment and the patient followed according to the study protocol.

Any AE events occurring up to 72 hours after the study drug is discontinued will be considered a treatment-emergent adverse event.

All SAEs, except for those anticipated events listed above, occurring from signed informed consent through study completion will be captured on the AE eCRF. Unless exempted as described above, all SAEs, whether or not deemed drug-related or expected, must be reported to the IRB by the investigator or qualified designee within 24 hours of first becoming aware of the event. For this study, all-cause deaths will be reported on the AE eCRF. The investigator or qualified designee will enter the required information regarding the SAE into the appropriate module of the eCRF. If the eCRF system is temporarily unavailable, the event, including the investigator-determined causality to study drug should be reported via the back-up paper AE form. Upon return of the availability of the electronic data capture (EDC) system, the SAE information must be entered into the eCRF.

Follow-up

When additional relevant information becomes available, the Investigator will record follow-up information according to the same process used for reporting the initial event as described above. The Investigator will follow all reportable events until resolution, stabilization or the event is otherwise explained.

The investigator will follow all SAEs until resolution, stabilization, until otherwise explained or until the participant completes the final follow-up, whichever occurs first. Investigators are also responsible for promptly reporting AEs to their reviewing IRB/EC in accordance with local requirements.

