7.3 Study Intervention Phase

Study treatment will be using the target dose of apixaban 5mg po BID or warfarin po daily for a goal INR of 2.0 to 2.5. All patients will be treated with aspirin 81mg daily as per the IFU. Randomized participants will receive the first dose of study drug as follows:

- LVAD patients randomized to warfarin will begin treatment once all anticipated surgical procedures are complete and the patient is deemed stable for transfer out of the ICU. Warfarin will be overlapped with low intensity heparin until the INR is at least 2.0. Warfarin will be dosed to maintain an INR goal of 2.0-2.5. For ambulatory LVAD patients, warfarin therapy will be continued.
- LVAD patients randomized to apixaban will transition from heparin to apixaban once all anticipated surgical procedures are complete and the patient is deemed stable for transfer out of the ICU. Heparin will be discontinued at the same time apixaban is initiated. For ambulatory LVAD patients on warfarin, warfarin will be transitioned to apixaban when the INR < 2.0.

Dose adjustments of apixaban will not occur. Dose adjustments of warfarin will be made no less than every 4 weeks to achieve the goal INR of 2.0 to 2.5. Participants will return to clinic according to the schedule shown in Appendix C.

For patients upgraded on the transplant list from a status 4 or below to a status 1-3, apixaban will be transitioned to warfarin, to allow for drug reversal at time of transplant. Patients randomized to the apixaban arm will be replaced to ensure 20 LVAD patients are exposed to apixaban over the duration of the study. Warfarin patients will not be replaced, as warfarin is standard of care therapy for LVAD patients.

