12 OUTCOME DETERMINATIONS

12.1 Primary Endpoint

Freedom from death or hemocompatibility related adverse events (stroke, device thrombosis, bleeding, aortic root thrombus and arterial non-CNS thromboembolism) at 24-weeks.

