17.2 Study Termination

The study may be terminated by the Sponsor at any time with suitable written notice to the reviewing IRB and applicable regulatory agencies. The study may be terminated by the DSMB based on concerns for significant harm to study participants based on criteria outlined in the DSMB charter. The following clinical events in the apixaban arm will result in an immediate pause of study enrollment for an evaluation by the independent DSMB:

- ≥ 2 thromboembolic events (ischemic stroke, arterial non-CNS embolism, device thrombosis, aortic root thrombus)
- ≥ 4 major bleeding events (Types 3-5)
- ≥ 2 deaths due to either thromboembolic events or major bleeding events

Patients who are already enrolled in the study will continue study-related activities during the enrollment pause.

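### Section 14.1.8 treats a hemorrhagic stroke on apixaban as a thromboembolic failure and omits aortic root thrombus, unlike the list in section 17.2 for the same arm

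*Combined protocol and SAP*

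**What the plan says.** Section 14.1.8 sets the treatment rule for the individual patient. On apixaban: "For patients in the apixaban arm with a thromboembolic event (stroke, device thrombosis or arterial non-CNS thromboembolism), will be considered a study drug failure". Such a patient leaves active treatment and goes onto warfarin; no INR goal is given for this conversion. For the other arm: "For patients in the warfarin arm with a thromboembolic event, will be managed with a higher INR goal of 2.5 to 3.0". That sentence carries no list of events.

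The same section has a separate bleeding rule, stated for each arm: "For patients experiencing a bleeding event, the aspirin will be discontinued". For apixaban, stopping the drug is then restricted to recurrent cases, in these words: "patients with recurrent bleeding will the apixaban be discontinued (withdrawn from active treatment) and warfarin initiated at an INR goal of 1.5 to 2.0".

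Section 17.2 sets the trigger that pauses enrollment, again for the apixaban arm: "≥ 2 thromboembolic events (ischemic stroke, arterial non-CNS embolism, device thrombosis, aortic root thrombus".

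The primary endpoint in 12.1 is "Freedom from death or hemocompatibility related adverse events (stroke, device thrombosis, bleeding, aortic root thrombus and arterial non-CNS thromboembolism) at 24-weeks". Aortic root thrombus is therefore a component in its own right, and Appendix B defines it separately from device thrombosis. Appendix B also defines stroke to include both ischemic and hemorrhagic causes, and its bleeding entry sends CNS bleeding to the stroke category. Section 7.3 gives the general treatment targets: "target dose of apixaban 5mg po BID or warfarin po daily for a goal INR of 2.0 to 2.5".

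**The concern.** One term, used for one arm, has two definitions, and the treatment rule has the less suitable one. Calling a brain bleed thromboembolic attaches the wrong management logic to it: a conversion written for clotting events and, if the list reaches the warfarin arm, a higher INR goal after a hemorrhage. Conversely, an event that is plainly thrombotic, and that the sponsor considers serious enough to count toward a pause, has no stated consequence for the apixaban patient who has it.

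The stake is mainly patient safety and consistent handling. There is also a reporting cost. Section 15.2 says that each patient's data will be reviewed individually and that the results will inform phase III design. A hemorrhagic stroke labelled a thromboembolic drug failure, or a root thrombus not labelled one, would distort that descriptive account.

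**Working it through.** No arithmetic applies, and the plan has no figure to reproduce. The check is a comparison of the two apixaban-arm lists, using the Appendix B definitions.

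| Event | Thromboembolic in 14.1.8 | Thromboembolic in 17.2 | Primary-endpoint component (12.1) |
|---|---|---|---|
| Ischemic stroke | yes | yes | yes, as stroke |
| Hemorrhagic stroke | yes, because stroke is unqualified | no | yes, as stroke |
| Device thrombosis | yes | yes | yes |
| Arterial non-CNS embolism | yes | yes | yes |
| Aortic root thrombus | no | yes | yes |

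Section 14.1.8 names 3 items and 17.2 names 4. Two event types are classified differently.

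**Hemorrhagic stroke, as written.** Appendix B makes stroke cover hemorrhage and files CNS bleeding there. Under 14.1.8 the apixaban patient is then a thromboembolic failure and moves to warfarin. The section sets a goal of 1.5-2.0 for conversion after recurrent bleeding and a goal of 2.5-3.0 for warfarin-arm thromboembolic events, but none for this conversion. A reader could fall back on the general 2.0-2.5 in 7.3; that is an assumption. In the warfarin arm, if the same list is taken to apply, the goal rises to 2.5-3.0 after a brain bleed.

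**Hemorrhagic stroke, if stroke means ischemic only.** Support for this reading is that the word stands under a thromboembolic label, that 17.2 says ischemic, and that the secondary endpoints separate the two types. A brain bleed must then be governed by the bleeding rule or by nothing. If the bleeding rule covers CNS bleeding, a first event stops aspirin and apixaban continues until bleeding recurs. This reading removes the misclassification but supplies no suitable rule.

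**Aortic root thrombus.** The other definitions do not bring it into 14.1.8. Device thrombosis concerns the pump, cannula, conduit or grafts. Arterial non-CNS thromboembolism requires an acute perfusion deficit. A thrombus seen on imaging in the root, cusp or valve that has not embolized meets neither. Two such events would pause enrollment under 17.2, yet neither patient would have a stated switch under 14.1.8.

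**Effect on the primary analysis.** Both events are components of the composite, so each has already counted when treatment changes. The discrepancy does not alter that patient's primary outcome.

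**The case against.** The strongest reply is that the sections do different jobs, one managing a patient and the other pausing enrollment, so their lists need not match. That is true, and the two sections do not give opposing orders. It does not explain why one term has two meanings, and the hemorrhagic-stroke problem arises from 14.1.8 and Appendix B without any reference to 17.2.

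A second reply is that investigators retain judgment. Section 18.4 lets the investigator withdraw a patient for any untoward effect, and omission from a mandatory-switch list does not forbid a switch. There is also only one center, which limits divergence. These points reduce the risk, but they do not supply the missing rule.

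Several stronger readings are tempting and are not supported:

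- *A reader might infer two equal and opposite instructions after a brain bleed.* The readings are not equal. Appendix B favors conversion. The alternative must narrow stroke against its definition and then return CNS bleeding to the bleeding rule. Some ambiguity remains, because the filing of CNS bleeding under stroke may be only a recording instruction.
- *A reader might take "Dose adjustments of apixaban will not occur" in 7.3 to bar holding apixaban.* It concerns dose. Section 14.1.4 contemplates interruption of the investigational product.
- *A reader might measure the problem as a distance between INR goals.* The goal after conversion is unstated, and 2.5-3.0 is written for the warfarin arm only, so such a difference would rest on a borrowed goal.
- *A reader might charge the warfarin arm with two faults at once:* a raised goal after a brain bleed, and a rule for root thrombus that apixaban lacks. The first requires the apixaban list to carry over; the second requires that it does not. Both cannot hold.

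**Conclusion.** The concern holds and should be fixed. Two event types are handled inconsistently. Hemorrhagic stroke is, as written, a thromboembolic failure that leads to warfarin at no stated goal. Aortic root thrombus counts toward the pause and the primary endpoint but triggers no stated switch.

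The first conclusion rests on giving stroke its Appendix B meaning. The warfarin-arm consequence rests on the further assumption that the apixaban list governs that arm. The continuation of apixaban after a first brain bleed rests on reading stroke as ischemic and on the bleeding rule reaching CNS bleeding.

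The documents give no rates for these two events, so no number of affected patients can be stated. A reader might infer bias in the primary comparison; the documents do not support that, since either event has already been counted and the analysis is by randomized arm. The problem concerns patient management and the labelling of drug failures.

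**What to change.** In 14.1.8, use the 17.2 list for both arms: ischemic stroke, device thrombosis, aortic root thrombus, and non-CNS arterial thromboembolism. Add that a hemorrhagic stroke is not a thromboembolic event, stops aspirin, never raises the INR goal, and is not handled by the first-bleed rule under which apixaban continues. If the sponsor does not want aortic root thrombus to force a switch, 14.1.8 should say so.

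The cost is a protocol amendment. Because it changes a treatment rule it is not merely administrative, and sections 14.1 and 18.2 require IRB approval. Making root thrombus a conversion trigger could also add a few apixaban conversions and, through the replacement provisions in 7.3 and 14.1.8, a few replacement patients. The documents give no rate from which to estimate how many. No visits or tests are added.

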18.4 Subject Withdrawal

Subjects may withdraw consent at any time for any reason or be dropped from the trial at the discretion of the investigator should any untoward effect occur. In addition, a subject may be withdrawn by the investigator or the Sponsor if enrollment into the trial is inappropriate, the trial plan is violated, or for administrative and/or other safety reasons. Should the subject be withdrawn from the study, the reason for withdrawal must be documented in the CRF.

Subjects who discontinue/withdraw from treatment prior to completion of the treatment regimen should be encouraged to continue to be followed for all remaining study visits.

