19.2 Appendix B - Adverse Event Definitions

- Arrhythmias: Any documented arrhythmia that results in clinical compromise, or requires hospitalization or treatment. Arrhythmias will be further classified as sustained ventricular arrhythmia or sustained supraventricular arrhythmia
- Arterial non-CNS thromboembolism: Acute systemic arterial perfusion deficit in any non-cerebrovascular organ system due to thromboembolism confirmed by 1 or more of the following: 1) standard clinical and laboratory testing, 2) operative findings, 3) autopsy findings
- Bleeding: the location/source of the bleed will be recorded and subsequently categorized as follows; CNS bleeding will be captured under cerebrovascular event/stroke
 - Type 2: Any overt, actionable sign of hemorrhage that does not fit the criteria for Type 3, 4, or 5 but does meet at least one of the following criteria:
 - 1) requiring non-surgical, medical intervention by a healthcare professional
 - 2) leading to hospitalization or increased level of care; or
 - 3) prompting evaluation
 - Type 3a
 - Overt bleeding accompanied by hemoglobin drop of 3 to < 5 g/dL
 - Any transfusion with overt bleeding
 - o Type 3b
 - Overt bleeding plus hemoglobin drop 5 g/dL or greater
 - Cardiac tamponade
 - Bleeding requiring surgical intervention for control (excluding dental/nasal/skin/hemorrhoid)
 - Bleeding requiring intravenous vasoactive agents
 - Type 4: VAD implantation-related bleeding (includes concomitant cardiac or non-cardiac surgical procedure)
 - Reoperation after the closure of incision or incisions used to implant the VAD to control bleeding
 - ≥ 50 kg: ≥ 4U pRBC within any 48 hours during the first 7 days postimplant
 - < 50 kg: ≥ 20 cm³/kg pRBC within any 24 hours during the first 7 days post-implant
 - Chest tube output > 2 liters within 24 hours
 - Type 5a: Probably fatal bleeding; no autopsy or imaging confirmation but clinically suspicious
 - Type 5b: Definite fatal bleeding; overt bleeding or autopsy or imaging confirmation
 - o For all types of bleeding, the event will be classified as:
 - Patient-related (e.g., coagulopathy unrelated to surgical technique such as non-adherence with anticoagulation medication resulting in inappropriately high level of anticoagulation, hepatic failure)
 - Management-related (e.g., related to surgical technique, hypertension, bleeding in the setting of inappropriate levels of anticoagulation)

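### The rule converting apixaban patients to warfarin after a thromboembolic event (14.1.8) omits aortic root thrombus, which 17.2 classes as thromboembolic in the same arm

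*Combined protocol and SAP*

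**What the plan says.** Section 14.1.8 sets the patient-level rule for the apixaban arm. A patient with a "thromboembolic event (stroke, device thrombosis or arterial non-CNS thromboembolism), will be considered a study drug failure and converted to warfarin". Such patients stay in scheduled follow-up.

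Section 17.2 sets the arm-level rule. Enrollment pauses for review by the data and safety monitoring board once the apixaban arm has two or more "thromboembolic events (ischemic stroke, arterial non-CNS embolism, device thrombosis, aortic root thrombus").

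Section 12.1 defines the primary endpoint as freedom at 24 weeks from death or from "stroke, device thrombosis, bleeding, aortic root thrombus and arterial non-CNS thromboembolism". Sections 4.2 and 12.2 also make survival free of aortic root thrombus a secondary endpoint.

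For the comparator, 14.1.8 says: "For patients in the warfarin arm with a thromboembolic event, will be managed with a higher INR goal of 2.5 to 3.0". That sentence does not list the qualifying events.

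**The concern.** The two rules use the same term for the same arm but list different events. An aortic root thrombus on apixaban is serious enough to be one of the two events that pause enrollment. Yet the rule that decides what happens to the individual patient does not mention it.

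At stake is the management of a patient with a known thrombus on an anticoagulant whose device-thrombosis and stroke risks in this population are, by the protocol's own account in the risk summary (section 10), not known. Section 7.3 rules out changing the apixaban dose, so conversion is the only protocol response to a thrombotic event in that arm. If the root thrombus later embolizes and causes a stroke or a peripheral event, conversion becomes mandatory, but only after the harm has occurred. In an open-label trial, leaving the decision to individual judgment also means that similar patients may be handled differently.

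**Working it through.** No arithmetic in the plan bears on this point, and the plan states no figure to reproduce. The check is a comparison of lists and definitions.

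**Step 1. Compare the lists.**

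| Event | 14.1.8 apixaban (convert) | 17.2 apixaban (pause) | 12.1 (primary endpoint) |
|---|---|---|---|
| Stroke | Yes | Ischemic only | Yes |
| Device thrombosis | Yes | Yes | Yes |
| Arterial non-CNS thromboembolism | Yes | Yes | Yes |
| Aortic root thrombus | **No** | Yes | Yes |

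Section 17.2 names four thromboembolic types, and 14.1.8 covers three of them. The only one missing is aortic root thrombus. The warfarin-arm sentence in 14.1.8 has no list to compare.

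**Step 2. Ask whether a root thrombus enters the 14.1.8 list through another definition.** Appendix B (19.2) defines aortic root thrombus as its own event: thrombus on the aortic valve, in a cusp or in the root, seen on echocardiography or CT. Against each listed event:

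- Device thrombosis, suspected or confirmed, concerns thrombus on device components (pump, cannula, conduit or grafts). The native valve and root are not among them.
- Arterial non-CNS thromboembolism requires an "Acute systemic arterial perfusion deficit in any non-cerebrovascular organ system due to thromboembolism". A thrombus that has not embolized has caused no such deficit.
- Stroke is a cerebrovascular accident. An isolated root thrombus is not one.

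So an isolated root thrombus meets none of the three. One that embolizes would trigger conversion through the resulting event.

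**Step 3. Look for another rule that requires a response.** Under 18.4 a subject may "be dropped from the trial at the discretion of the investigator should any untoward effect occur". That permits action but does not require conversion, and it speaks of leaving the trial, whereas 14.1.8 converts the patient and keeps follow-up going. Section 14.1.7 provides for recording events that lead to a change in antithrombotic dosing but does not say which events should lead to one. Section 15.2 has each patient's data reviewed individually, and 17.1 has the board review cumulative data. Neither prescribes treatment.

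**Step 4. Check what is not affected.** Sections 12.1, 12.2 and 17.2 all name the event, and 15.1 attributes endpoints by randomized arm whatever treatment follows. Counting and analysis therefore do not depend on whether the patient was converted.

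**The case against.** The strongest reply is that the lists serve different purposes. Section 17.2 is a sensitive trigger for board review, while 14.1.8 declares drug failure in an individual. Whether an isolated root thrombus should force conversion is a clinical judgment, and the shorter list may be deliberate. Nor does the text say outright that the parenthesis is exhaustive. Part of this stands: the documents do not show that the omission was a mistake. But the parenthesis has no marker of illustration, although the exclusion criteria in 8.3 mark their examples as such, and no reason is given for leaving out an event that 17.2 calls thromboembolic. If the omission is intended, the protocol should say so.

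A second reply is that the event would not go unnoticed and the investigator can act. That is true, and it limits the weight of the point. A reader might infer that 14.1.8 obliges the patient to remain on apixaban; it does not, since nothing forbids stopping the drug.

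A reader might also infer that the warfarin-arm sentence directs a higher INR goal after a hemorrhagic stroke, because Appendix B defines stroke as any cause and states that "CNS bleeding will be captured under cerebrovascular event/stroke". The sentence says thromboembolic, however, and the plain meaning of that word excludes hemorrhage. This is a matter of wording, not a demonstrated hazard.

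The Executive Summary leaves root thrombus out of its hypothesis and its secondary list but includes it in its primary endpoint. That is a wording note only; it does not govern treatment under 14.1.8.

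**Conclusion.** The point holds as a gap in a stated patient-level safety rule. Followed as written, 14.1.8 requires no change of anticoagulant for an apixaban patient with an isolated aortic root thrombus, although 17.2 classes the event as thromboembolic in that arm. One such event is half the pause threshold (1 of 2).

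The size is modest: one event type of four, investigator discretion preserved, and an effect on management and consistency only. A reader might infer bias in the primary comparison, but the event is counted in the same way whether or not the patient is converted. No number of affected patients can be given. The documents state no frequency, and Appendix C schedules no echocardiography or CT, so neither how often nor when the event would be found can be derived.

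The conclusion assumes that the parenthesis in 14.1.8 defines the triggering events and that the thrombus has not embolized. It should be corrected.

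**What to change.** 1. Add aortic root thrombus to the apixaban drug-failure list in 14.1.8.
2. State that the warfarin-arm sentence applies to the same thromboembolic events, including aortic root thrombus, and that stroke in the rule raising the INR goal means ischemic stroke.

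This takes one phrase and one clause, with no new visits, imaging or case report form fields. The downside is an occasional additional conversion to warfarin. Section 14.1.8 says "Each apixaban patient who does not complete the 6-month study duration will be replaced". It is not explicit whether a converted patient who remains in follow-up counts as not completing. If so, one such patient means 20 + 1 = 21 randomized to apixaban. A second root thrombus in that arm would itself reach the pause threshold in 17.2.

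If the investigators prefer not to mandate conversion, the alternative is one sentence in 14.1.8 saying that root thrombus is deliberately left to clinical judgment, and why.
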